5.6.2. Laboratory, Vital Signs, and Physical Examinations

Hematology, Chemistry and Urinalysis tests will be performed locally within 72 hours of blood sample collection, according to the Schedules of Activities (CTP 1.3), at Screening (optional, at the discretion of the investigator), at Day 1 (pre-dose): Day 8, Day 15, Day 29 and at delivery (postpartum 1) and postpartum 43 (42 days after delivery). For further details on all laboratory assessments refer to CTP 8.2.3.

Continuous laboratory variables will be summarized using the following statistics, as appropriate: number of observations, arithmetic mean (mean), standard deviation (SD), standard error (SE), median, minimum, and maximum. Frequencies and percentages (one decimal place) will be generated for categorical laboratory variables. Denominator for the percentages is the number of participants in the considered population and phase for a certain regimen (incidence per 100 participants/phase).

For all adult participants, weight and height (and BMI) at baseline will be summarized using descriptive statistics. Physical exam will be summarized and listed for adults. Neonatal physical and birth exam will be summarized and listed for neonates.

Vital signs for adults and neonate/infants including temperature, pulse/heart rate, respiratory rate, blood pressure (adult participants only: systolic and diastolic) and blood oxygen saturation will be summarized over time, using descriptive statistics. Abnormalities emerging after vaccination will be tabulated by worst abnormality grade using the FDA table in Section 6.6.

Temperature will be measured at each scheduled time point and summarized using descriptive statistics. A listing of participants with fever will be provided for adults and neonates. Other vital signs abnormalities will be listed with corresponding grade.

For adult COVID-19 cases, temperature will be summarized over time for the duration of followup of COVID-19 episodes, using descriptive statistics.

All parent(s)/caregiver(s) of neonates/infants with (suspected) COVID-19 should measure blood oxygen saturation and body temperature.

An abnormality (toxicity grade or abnormality based on normal ranges) will be considered as emerging in a particular period if it is worse than the baseline value. If the baseline is missing, the abnormality is always considered emerging. A shift from 'abnormally low' at baseline to 'abnormally high' post baseline (or vice versa) is also emerging. In case a laboratory test result is censored (no numeric value is available, but only a verbatim term) then a numeric value will be imputed by a value exceeding the cut-off value with one unit. (<x: subtract 1 unit from x, >x: add 1 unit to x: e.g., <3.45 is imputed with 3.44, <90 with 89 and >101 with 102).

In case no toxicity grades are defined for a test, the abnormalities (above/below normal range) will be used. In determining toxicity grades, the following rules are applied:

- worst grades/abnormalities are determined over the whole observational period for each trial period separately, including all post-baseline measurements of that period.
- The abnormalities 'abnormally low' and 'abnormally high' are considered equally important, i.e. if a participant has as well an abnormally low as an abnormally high value post-baseline, both abnormalities are shown in the tables. (This means that the sum of the percentages can be more than 100%).
- Note: as the grading scale for some parameters in the grading table has some gaps (zones where no toxicity grade definition exists), results falling in these zones will be allocated to the adjacent worst-case grade. For example if a laboratory result falls within the 'grey area' between the ranges for 'Grade 1' and 'Grade 2' in the FDA table, then this result would be allocated to 'Grade 2' (the adjacent worst-case grade).
- If a value falls within the grading as specified in the grading FDA table but using the local laboratory it falls within normal limits, the value is considered as normal. For example, if the local lab classifies a result as 'normal' within their prespecified limits, then the value can indeed be considered normal even when according to the FDA table it would be 'Grade 1'.

For the grades, no distinction will be made between test results of samples obtained under fasting and under non-fasting conditions.

The following physical examinations will be performed: full and targeted examination, obstetric examination, obstetric ultrasound, targeted physical examination, neonatal birth examination (physical and Apgar score) and infant examination. Physical examination findings will be summarized at baseline (adult participants) and at each timepoint for neonates/infants. A listing of the abnormalities will be made. Apgar score findings will be summarized and listed separately.

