5. STATISTICAL ANALYSES

5.1. General Considerations

A baseline (or reference) value will be defined as the value of the last available assessment prior to the first vaccination on Day 1, where Day 1 is the date of first vaccination for adults. A value at birth is baseline value for neonates and the birth date is the neonate reference date. The neonate baseline values for immunogenicity analysis are those from the cord blood sample collected.

Every adult will have a unique subject ID in the ADaM datasets and every neonate will have the same unique subject ID with 'A' added at the end of the ID. Multiple pregnancies [twins or higher order multiples] are excluded from the study but if a participant with multiple pregnancy is inadvertently enrolled, neonates will have the same unique subject ID with 'A', 'B', 'C' and D added at the end of the ID based on the number of neonates.

Unless otherwise specified, continuous variables will be summarized using the following statistics, as appropriate: number of observations, arithmetic mean (mean), standard deviation (SD), standard error (SE), median, minimum, and maximum. Frequencies and percentages (one decimal place) will be generated for categorical variables. Denominator for the percentages is the number of participants in the considered population, and phase (where applicable; incidence per 100 participants/phase).

No formal statistical testing is planned. The safety analysis will be performed on the FAS-A based on actual intervention received and the FAS-NVN, unless otherwise specified. Safety data will be presented by period/phase (as applicable) as well as over the entire study. Immunogenicity results will be conducted on the PPI-A and PPI-NVN and presented per scheduled time point as appropriate. Safety and immunogenicity endpoints will be summarized descriptively by previous vaccination group (as defined in Section 1.2) and overall. All listings will include the previous vaccination group. Vaccination schedule in Group 4 (i.e. vaccine-naive at study entry) will have two components: the Primary Vaccination and the (optional) Booster Vaccination. Listings will be shown per phase and time point, as appropriate.

Participants that took another COVID-19 vaccine during the study are excluded from all safety and immunogenicity analyses from the moment they received the other vaccine. The safety data from those participants after they received the other vaccine will be listed separately.

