Other exploratory or sensitivity analyses, on an ad-hoc basis, may be performed in addition to the analyses described in this document.

For adults, study Day 1 or Day 1 refers to the start of the first study vaccination. For neonates, study Day 1 or Day 1 refers to the neonate birth. Unless specified otherwise, safety assessments at all visits will be assigned a day relative to those dates (respectively for adults and neonates). In addition, in Group 4, safety assessments occurring after the booster vaccination date will also be assigned a day relative to this date.

Study day and relative day are defined as follows:

For adults (Day 1 refers to the start of the first study vaccination):

- Study Day=visit date-date of Day1+1; if visit date ≥ date of Day 1
- Study Day=visit date-date of Day1; if visit date < date of Day 1

For neonates (Day 1 refers to the neonate birth):

- Study Day=visit date-neonate birth date+1; if visit date \geq date of Day 1
- Study Day=visit date-neonate birth date+1; if visit date < date of Day 1

Relative day (relday), the number of days in the analysis time point will be defined as:

- relday = visit date reference date+1 for visits on or after the reference date,
- *relday = visit date reference date* for visits before the reference date,

where the reference date equals the date of the first study vaccination for adults, and as well as the date of booster vaccination for participants in Group 4, and the neonate birth date for the neonates.

For laboratory and vital signs all time points (including unscheduled ones, if any) are also considered in the determination of the worst toxicity grade.

Unscheduled results or multiple results for laboratory and vital signs taken at the same visit will be reported in listings.

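### Laboratory abnormality percentages are divided by everyone in the phase, so in phases with no listed scheduled sample unsampled women count as having no abnormality

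*SAP*

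**What the plan says.** Section 5.6.2 covers the laboratory tables. "Frequencies and percentages (one decimal place) will be generated for categorical laboratory variables", and the rule for them is: "Denominator for the percentages is the number of participants in the considered population and phase for a certain regimen". Nothing requires that a participant has a result. Section 5.1 sets the same kind of default for all percentages: "Denominator for the percentages is the number of participants in the considered population, and phase", where a phase applies.

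The numerator is built differently. Section 5.6.2 says that "worst grades/abnormalities are determined over the whole observational period for each trial period separately, including all post-baseline measurements of that period". Section 5.1 adds unscheduled results: "For laboratory and vital signs all time points (including unscheduled ones, if any) are also considered" when the worst grade is determined.

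Apart from an optional screening sample, section 5.6.2 schedules laboratory tests "at Day 1 (pre-dose): Day 8, Day 15, Day 29 and at delivery (postpartum 1) and postpartum 43 (42 days after delivery"). It refers to the protocol for the full schedule.

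Table 3 defines the phases. Post-dose 1 ends at the latest at 23:59 on the vaccination date plus 28 days, and earlier if birth, a booster or an outside COVID-19 vaccine comes first. Prepartum follow-up 1 then runs at the latest to one minute before birth or termination. Postpartum follow-up 1 runs from birth for 42 days. Post-dose 2 and Booster follow-up 1 and 2 start from the booster. Section 5.1 says that safety data are shown by phase where applicable, and also over the entire study.

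**The concern.** Numerator and denominator refer to different people. A woman can enter the numerator only if she was sampled in the phase, but she enters the denominator merely by being in it. An unsampled woman is thus reported as having no abnormality, when nothing is known about her.

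The rule in section 5.6.1.5, that someone who reports no event has none, sits under adverse events. It is reasonable there because adverse events are collected by report. It does not carry over to a test that was never done.

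The study is descriptive and tests no hypotheses (section 2), so the tabulated percentages are themselves the result. Platelet counts also bear on thrombocytopenia, which is part of the adverse events of special interest. If by-phase laboratory tables include phases without scheduled sampling, those phases would look cleaner than Post-dose 1 only because fewer women were tested. The comparison most exposed is Post-booster against Post-dose 1, which section 5.1.2 names together as active periods.

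**Working it through.** The SAP gives no laboratory abnormality rate, so there is no figure of its own to reproduce. The check has three steps.

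**1. Place the listed samples in the phases**

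With day = date − reference date + 1, vaccination + 28 days is Day 29, and birth + 42 days is postpartum Day 43.

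| Phase (Table 3) | Scheduled samples listed in 5.6.2 |
|---|---|
| Post-dose 1 | Days 8, 15 and 29, if on time and before birth |
| Prepartum follow-up 1 | None; only a late Day 29 sample, a delivery sample drawn before birth, or an unscheduled test |
| Postpartum follow-up 1 | Delivery; postpartum 43 is on the boundary |
| Postpartum follow-up 2 | Postpartum 43, if placed here |
| Post-dose 2 | None tied to the booster; postpartum 43 could fall here by chance |
| Booster follow-up 1 and 2 | None listed |

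The boundary is inconsistent within Table 3. Postpartum follow-up 1 ends at birth + 42 days, which is Day 43, but its label stops at Day 42 and follow-up 2 is labelled from Day 43. A Day 29 visit held one day late moves into Prepartum follow-up 1. Section 5.1.3 accepts Day 29 immunogenicity samples within 10 days either side, so such shifts are expected.

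**2. Effect of the denominator**

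Let N be the women in the phase, n those with at least one result in it, p the abnormality rate among the n, and f = n/N. Then

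reported percentage = (p × n)/N = p × f.

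The SAP gives neither p nor f, so the values below are assumptions.

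| p | f = 0.02 | f = 0.10 | f = 0.50 | f = 0.90 | f = 0.95 |
|---|---|---|---|---|---|
| 10% | 0.2% | 1.0% | 5.0% | 9.0% | 9.5% |
| 20% | 0.4% | 2.0% | 10.0% | 18.0% | 19.0% |

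The low values of f suit phases without a scheduled sample, and the high values phases with one. A value of 0.50 could arise in Postpartum follow-up 2 if the postpartum 43 samples split across the boundary.

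**3. Size of the dilution in Post-dose 1 from early delivery**

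A woman who delivers before Day 8 has no scheduled post-dose sample in Post-dose 1. Assume entry E uniform from week 28 to week 38 (or 39, if week 38 means 38 completed weeks), and delivery D normal with mean 39.3 weeks and SD 1.6. None of these distributional inputs is in the SAP. Only women still pregnant at vaccination count:

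share = P(E < D < E + 1 week) / P(D > E)

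- Entry to week 38: 0.0311 / 0.981 = 3.2%
- Entry to week 39: 0.0499 / 0.955 = 5.2%

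If these women are the only ones unsampled, a 10% rate is shown as 10% × (1 − 0.032) = 9.7%, or 10% × (1 − 0.052) = 9.5%.

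**The case against.** The strongest reply is that the impact is limited and partly conditional. The metric is openly labelled as incidence per 100 participants per phase, counts accompany the percentages, and the entire-study summary, where almost everyone has a result, barely changes. By-phase display is promised only where applicable, output detail is left to the data presentation specifications, and the full sampling schedule is in the protocol. All of this stands. It limits the size of the problem but does not repair the stated rule.

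A second objection concerns the remedy, and it also stands. Unscheduled tests may come from routine care or adverse event work-up, so the women tested may be selected towards abnormal results. Dividing by women with a result would then overstate the rate: two abnormal results among three women tested would read as 67%. For the same reason, p × f describes what the table shows and does not recover the true rate.

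Stronger readings are tempting but not supported:

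- A reader might infer that any phase with few samples reports near zero. One scheduled sample per woman is enough to bring f close to 1.
- A reader might infer that a false fall after Day 29 is certain. It arises only if those phases are tabulated, and its size depends on unscheduled and late samples whose frequency is not given.
- A reader might put early delivery before Day 8 at about 9.5% of the later stratum. That figure appears only with entry to week 39 and with simulated deliveries before vaccination counted, which is impossible here.
- A reader might extend the point to N-serology and ASQ-3 percentages. Those sections state no denominator of their own, so the extension rests only on the general default in 5.1.

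**Conclusion.** The point holds for phases with no listed scheduled sample: Prepartum follow-up 1, and the booster phases unless the protocol schedules laboratory visits after the booster. Any percentage shown there is the rate among sampled women times the share sampled, for example 10% shown as 1% if 10% are sampled (an assumption), and cannot be set beside Post-dose 1. Phases with a scheduled sample are only slightly diluted. Early delivery accounts for about 3% to 5% of the 28 to 38 week stratum under the assumed entry and delivery distributions, so 10% becomes about 9.5% to 9.7%. The entire-study summary is little affected. This is a clear fault in a stated rule, moderate in consequence and cheap to correct.

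**What to change.** In section 5.6.2:

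1. Define the denominator for categorical laboratory percentages as the participants with at least one post-baseline result for that parameter in that phase, and show that N in each table.
2. Do not tabulate percentages for phases without scheduled laboratory sampling. List their unscheduled abnormalities instead, so that selective testing does not inflate a rate.
3. Reconcile the end of Postpartum follow-up 1 in Table 3 with its label, and state which phase the postpartum 43 sample belongs to.
4. Assign a late Day 29 sample to Post-dose 1 only if it was taken before birth and before any booster or other COVID-19 vaccine. Allocation by nominal visit without this limit would put postpartum results into a period that Table 3 ends before birth.

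The cost is a change of SAP wording and of the denominator in the table programs; no new data are needed. Some percentages will rise, and denominators will differ between parameters, so the N must be read with each percentage.

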6.6. Appendix 6 FDA Toxicity Grading Scale for Vaccine Trials

Adapted from the FDA Guidance document "Toxicity Grading Scale for Healthy Adult and Adolescent Volunteers Enrolled in Preventive Vaccine Clinical Trials" (September 2007)

Local Reaction to Injectable Product	Mild (Grade 1)	Moderate (Grade 2)	Severe (Grade 3)	Potentially Life Threatening (Grade 4)
Pain/Tenderness [#]	Aware of symptoms but easily tolerated; Does not interfere with activity; Discomfort only to touch	Notable symptoms; Requires modification in activity or use of medications; Discomfort with movement	Incapacitating symptoms; Inability to do work, school, or usual activities; Use of narcotic pain reliever	Hospitalization; Pain/tenderness causing inability to perform basic self- care function
Erythema [#]	25 – 50 mm	51 – 100 mm	>100 mm	Hospitalization; Necrosis or exfoliative dermatitis
Swelling [#]	25 – 50 mm	51 – 100 mm	>100 mm	Hospitalization; Necrosis

A: Tables for Clinical Abnormalities

[#] Revised by the sponsor.

Vital Signs *	Mild (Grade 1)	Moderate (Grade 2)	Severe (Grade 3)	Potentially Life Threatening (Grade 4)
Fever (°C) ** (°F)**	38.0 - 38.4 100.4 - 101.1	38.5 - 38.9 101.2 - 102.0	39.0 - 40.0 102.1 - 104.0	>40 >104.0
Tachycardia - beats per minute	101 – 115	116 – 130	>130	Hospitalization for arrhythmia [#]
Bradycardia - beats per minute***	50 - 54	45 – 49	<45	Hospitalization for arrhythmia [#]
Hypertension (systolic) - mm Hg	141 – 150	151 – 155	>155	Hospitalization for malignant hypertension [#]
Hypertension (diastolic) - mm Hg	91 – 95	96 – 100	>100	Hospitalization for malignant hypertension [#]
Hypotension (systolic) – mm Hg	85 - 89	80 - 84	<80	Hospitalization for hypotensive shock [#]
Respiratory Rate – breaths per minute	17 – 20	21 – 25	>25	Intubation

* Participant should be at rest for all vital sign measurements.

** For oral temperature: no recent hot or cold beverages or smoking.

*** When resting heart rate is between 60 – 100 beats per minute. Use clinical judgement when characterizing bradycardia among some healthy participant populations, for example, conditioned athletes.

[#] Revised by the sponsor.

Systemic (General)	Mild (Grade 1)	Moderate (Grade 2)	oderate (Grade 2) Severe (Grade 3)	
Vomiting [#]	No interference with activity or 1 – 2 episodes/24 hours	Some interference with activity or >2 episodes/24 hours	Prevents daily activity, requires outpatient IV hydration	Hospitalization; Hypotensive shock

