* The laboratory values provided in the tables serve as guidelines and are dependent upon institutional normal parameters. Institutional normal reference ranges should be provided to demonstrate that they are appropriate.

** The clinical signs or symptoms associated with laboratory abnormalities might result in characterization of the laboratory abnormalities as potentially life-threatening (Grade 4). For example, a low sodium value that falls within a Grade 3 parameter (125-129 mEq/L) should be recorded as a Grade 4 hyponatremia event if the participant had a new seizure associated with the low sodium value.

***ULN is the upper limit of the normal range.

Hematology *	Mild (Grade 1)	Moderate (Grade 2)	Severe (Grade 3)	Potentially Life Threatening (Grade 4)
Hemoglobin (Female) - mg/dL	11.0 - 12.0	9.5 - 10.9	8.0 - 9.4	< 8.0
Hemoglobin (Female) change from baseline value - mg/dL	Any decrease – 1.5	1.6 - 2.0	2.1 - 5.0	> 5.0
Hemoglobin (Male) - mg/dL	12.5 - 13.5	10.5 - 12.4	8.5 - 10.4	< 8.5
Hemoglobin (Male) change from baseline value – mg/dL	Any decrease – 1.5	1.6 - 2.0	2.1 - 5.0	> 5.0
WBC Increase - cell/mm ³	10,800 - 15,000	15,001 - 20,000	20,001 - 25,000	> 25,000
WBC Decrease - cell/mm ³	2,500 - 3,500	1,500 - 2,499	1,000 - 1,499	< 1,000
Lymphocytes Decrease - cell/mm ³	750 - 1,000	500 - 749	250 - 499	< 250
Neutrophils Decrease - cell/mm ³	1,500 - 2,000	1,000 - 1,499	500 - 999	< 500
Eosinophils - cell/mm ³	650 - 1500	1501 - 5000	> 5000	Hypereosinophilic
Platelets Decreased - cell/mm ³	125,000 - 140,000	100,000 – 124,000	25,000 - 99,000	< 25,000
Prothrombin time (PT) – increase by factor	1.0 – 1.10 x ULN**	1.11 – 1.20 x ULN	1.21 – 1.25 x ULN	> 1.25 ULN
Partial thromboplastin time (PTT) – increase by factor	1.0 – 1.2 x ULN	1.21 – 1.4 x ULN	1.41 – 1.5 x ULN	> 1.5 x ULN
Fibrinogen increase - mg/dL	400 - 500	501 - 600	> 600	
Fibrinogen decrease - mg/dL	150 - 200	125 – 149	100 – 124	< 100 or associated with gross bleeding or disseminated intravascular coagulation (DIC)

* The laboratory values provided in the tables serve as guidelines and are dependent upon institutional normal parameters. Institutional normal reference ranges should be provided to demonstrate that they are appropriate.

** ULN is the upper limit of the normal range.

VAC31518 (JNJ-78436735)

Statistical Analysis Plan VAC31518COV2004 HORIZON 1

Urine *	Mild (Grade 1)	Moderate (Grade 2)	Severe (Grade 3)	Potentially Life = Threatening (Grade 4)

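### Section 5.6.2 does not limit vital-sign grading to adults, although the Section 6.6 scale is an adult and adolescent one; separately, the hemoglobin rows of that scale carry the wrong unit

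*SAP*

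**What the plan says.** The vital-signs paragraph of SAP Section 5.6.2 opens with its scope: "Vital signs for adults and neonate/infants including temperature, pulse/heart rate, respiratory rate, blood pressure (adult participants only: systolic and diastolic". Blood pressure is the only item restricted to adults. The next sentence sets the grading: "Abnormalities emerging after vaccination will be tabulated by worst abnormality grade using the FDA table in Section 6.6". The following short paragraph plans a fever listing for adults and neonates and then states: "Other vital signs abnormalities will be listed with corresponding grade".

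Section 6.6 names the source of its table as the "Toxicity Grading Scale for Healthy Adult and Adolescent Volunteers Enrolled in Preventive Vaccine Clinical Trials". The SAP contains no other grading scale for vital signs.

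Four related rules bear on this:

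- Section 5.1 puts the safety analysis on both the adult set (FAS-A) and the infant set (FAS-NVN) unless otherwise specified, and takes the birth value as the neonatal baseline.
- Section 5.6.2 counts an abnormality as emerging when it is worse than the baseline value, and always when baseline is missing.
- Section 5.6.2 lets a local normal range override a grade, but the rule is written for local laboratory limits.
- Section 1.2 states that neonates and infants receive no study vaccine.

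In the hematology part of Section 6.6, the first row is headed "Hemoglobin (Female) - mg/dL". The other three hemoglobin rows (female change from baseline, male absolute, male change) also carry mg/dL.

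**The concern.** A paragraph that covers newborns leads into a grading rule whose only scale was built for adults and adolescents. The authors did narrow the scope for blood pressure, so the absence of a similar limit on the grading reads as if infants are included. A programmer following the text would apply adult heart-rate and respiratory-rate limits to newborns. The resulting grades would reflect the infants' age rather than their condition. A listing full of Grade 3 entries in healthy infants could suggest a signal where there is none, or bury a real one.

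The hemoglobin label is a separate matter in the same appendix. Section 5.6.1.2 makes this table the severity standard for laboratory data, and hematology is measured through delivery and postpartum Day 43, so the unit affects the grading of maternal anemia.

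**Working it through.** The SAP states no figure on this point, so there is none to reproduce. The check applies the printed limits to example values.

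**Vital signs.** Limits from Section 6.6, rows "Tachycardia - beats per minute" and "Respiratory Rate – breaths per minute":

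| | Grade 1 | Grade 2 | Grade 3 | Grade 4 |
|---|---|---|---|---|
| Heart rate (/min) | 101-115 | 116-130 | >130 | hospitalization for arrhythmia |
| Respiratory rate (/min) | 17-20 | 21-25 | >25 | intubation |

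Assumption, not in the SAP: newborn respiratory rate 30-60/min and heart rate 100-160/min.

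- Respiratory rates of 26, 30, 40, 50 and 60 are all Grade 3. The whole assumed range lies above 25, so every infant is Grade 3. The result holds for any infant breathing faster than 25/min and does not depend on where in the range the true values lie.
- Heart rate 100 gives no grade, 110 is Grade 1, 120 and 130 are Grade 2, and 131, 140, 150 and 160 are Grade 3. The assumed range therefore splits: 101-130 is Grade 1 or 2, and above 130 is Grade 3. Extending the range to 180/min adds only Grade 3 values.

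**What each output would show if infants are included**

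- *Listing with grade.* The sentence has no emergence condition. All infants in the assumed range appear at Grade 3 for respiratory rate.
- *Emergent table, baseline available, grades compared.* An infant at Grade 3 at birth counts only on reaching Grade 4, which for respiratory rate means intubation. An infant with a birth heart rate of 130 or less who later exceeds 130 counts as emergent Grade 3.
- *Emergent table, baseline available, raw values compared.* The rule speaks of being worse than the baseline value, so this reading is not excluded. A rate of 40/min at birth and 45/min later would count as emergent Grade 3.
- *Emergent table, baseline missing.* Any graded value counts as emergent.

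None of these gives a grade that separates a healthy infant from an unwell one.

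**Hemoglobin.** Conversion: value in mg/dL = 1000 x value in g/dL. Female limits printed: absolute 11.0-12.0, 9.5-10.9, 8.0-9.4, <8.0; decrease any to 1.5, 1.6-2.0, 2.1-5.0, >5.0.

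| Finding | Limits read as g/dL | Limits read as printed, mg/dL |
|---|---|---|
| Level 7.0 g/dL | Grade 4 | 7000, above 12.0: no grade |
| Level 10.0 g/dL | Grade 2 | 10,000, above 12.0: no grade |
| Fall of 0.1 g/dL | Grade 1 | 100, above 5.0: Grade 4 |
| Fall of 1.8 g/dL | Grade 2 | 1800, above 5.0: Grade 4 |

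The two kinds of row fail in opposite directions. The local-normal-range rule might cancel a change grade where the level itself is normal, but the SAP does not say how it applies to the change rows. Albumin and total protein in the same appendix are in g/dL.

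**The case against.** The best counter-argument is the qualifier in the grading sentence. It speaks of abnormalities that emerge after vaccination, and infants are not vaccinated. Taken literally, the emergent table then concerns vaccinated adults only, and what infants clearly receive is a descriptive summary over time. The fever listing names neonates, while the sentence after it does not. This part stands: neonatal grading in the emergent table is a possible reading, not an explicit instruction. It does not settle the listing, whose sentence has no vaccination qualifier and follows directly on one that includes neonates. The default in Section 5.1 also brings in the infant set.

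A reader might infer that the emergent table would show all newborns at Grade 3. The text does not support that. If grades are compared, infants already at Grade 3 at birth drop out unless they reach Grade 4. The all-infants statement fits the listing, and only under the assumed ranges.

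A reader might also infer that neonatal safety as a secondary objective is compromised. The endpoints in Section 5.4.1 are SAEs including MIS-C, AESIs, MAAEs, AEs leading to discontinuation, and neonatal outcomes. Vital-sign grades are not among them, and no hypothesis is tested.

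On hemoglobin, limits such as 11.0-12.0 make sense only in g/dL, so this is most likely a label slip that a programmer would notice. The male rows have no bearing on pregnant participants. It would also be wrong to say that hemoglobin would never be graded under the printed unit, since that is true of the absolute rows only.

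**Conclusion.** The concern holds as a defect of scope. Section 5.6.2 leaves an adult and adolescent scale as the only grading rule for a paragraph that includes neonates, and nothing confines the table or the listing to adults. For the listing, the consequence under the assumed newborn ranges is Grade 3 for respiratory rate in every infant and Grade 3 for tachycardia in every infant above 130/min, with Grade 1 or 2 at 101-130/min. For the emergent table, inclusion of infants is ambiguous; if they are included, what it shows depends on the form of the baseline comparison and on missing birth values. The newborn ranges are outside assumptions, although the respiratory result needs only rates above 25/min. The effect is confined to a supportive neonatal safety display. Use of the scale for adult vital signs is not in question.

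The hemoglobin unit is a separate and definite error by a factor of 1000 in a severity table, probably typographical.

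**What to change.** - In Section 5.6.2, state that grading of vital signs by Section 6.6 applies to adult participants only, for both the emergent table and the listing.
- For neonates/infants, keep the planned descriptive summaries and fever listing. List other vital-sign values that fall outside age-specific reference limits, with the source of the limits named, or that the investigator marks as abnormal.
- In Section 6.6, change the unit of all four hemoglobin rows from mg/dL to g/dL.

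The cost is two sentences and a unit correction. No new data are needed, and no endpoint or analysis set changes.
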